## 9. CORRELATIVE/SPECIAL STUDIES

## 9.1 Rationale for Methodology Selection

9.1.1 Vaccine-induced seroconversion: Serum samples obtained at baseline and at follow-up study visits will be assessed for antibodies to HPV VLP types 6/11/16/18/31/33/45/52/58 by competitive Luminex immunoassay (HPV-9 cLIA Version 2.0). For the primary endpoint, a participant will be defined as seroconverted i.e., anti-HPV 6, 11, 16, 18, 31, 33, 45, 52, or 58 positive by Merck's proprietary competitive Luminex Immunoassay (cLIA) assay if the anti-HPV serum level at the 12-months posttransplant visit is  $\ge 30, \ge 16, \ge 20, \ge 24, \ge 10, \ge 8, \ge 8, \text{ or } \ge 8 \text{ milli Merck units (mMU)/mL, respectively}$ by the cLIA assay [21,23]. The cLIA assay uses a multiplex format with each of the nine virus like particle (VLP)-types in the vaccine fixed to Luminex microspheres with distinct fluorescent properties. Antibody titers are determined in a competitive format, where type-specific phycoerythrin (PE)-labeled, neutralizing monoclonal antibodies (mAbs-PE) compete with an individual's vaccine-induced antibodies in the serum for binding to conformationally-sensitive, neutralizing epitopes on the VLPs [23,24]. There is no specific (minimum) number of serotypes required for classifying someone as seroconverted, since the seroconversion for each vaccine-serotype will be assessed independently. Further, since the cLIA antibody titers to each HPV type are determined using type-specific monoclonal antibodies, it is not possible to make a direct comparison of assay results across HPV types. Given the age of the participants, there is high likelihood of having prior sexual exposure to some, if not all, individual HPV types targeted by the nonavalent HPV vaccine. However, anti-HPV antibodies induced due to such 'natural' infection are usually detected at a much lower titer levels than the aforementioned cutoffs defined for vaccineinduced seropositivity. Type-specific sensitivity analyses, restricted to participants who are seronegative for individual types at baseline, will also be conducted. Assays will be performed at Merck Research Laboratories. If access to cLIA is not feasible due to technical or operational reasons, a 9-valent multiplex HPV assay (based on same principle/framework as the cLIA assay) developed at the NCI Frederick National Laboratory for Cancer Research (FNLCR) will be used for the study.

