#### APPENDIX G

#### **COVID-19 Contingency Plan**

**Background**: In response to the public health emergency due to the COVID-19 pandemic, several adaptations have been included to ensure that the protocol will be able to meet its primary endpoint. This Appendix lists the specific modifications to the protocol that may be permitted to be undertaken in the context of the COVID-19 Contingency plans.

1. Remote Specimen Collection: Considering the closure of several study clinics to non-emergency study visits due to the COVID-19 crisis and concerns about SARS-COV2 transmission, an alternative plan for remote specimen collection will be offered to eligible and affected participants. This includes an at-home self-collection of a cervical/vaginal specimen that is described in the protocol and would also be self-collected in clinic. In addition, we include an at-home finger stick capillary blood collection of a dried blood spot via a novel sample collection device (Neoteryx Mitra cartridge). This device is based on volumetric absorptive microsampling (VAMS) technique that has been previously evaluated in measuring vaccine antibody responses and other biomarkers (See references below). Incorporating this device will allow the possibility of measurement of HPV antibody responses closer to the original/protocol-specified visit time points when COVID-19-related concerns preclude the possibility of in-person clinic visits. The procedures for remote specimen collection includes an addendum consent (APPENDIX H) for an at-home finger-stick capillary blood collection (dried blood spot) via a special collection device and return shipment of the specimen, along with phone calls to review medical and surgical history, medications, symptom assessment, determination of ECOG performance status and administration of study questionnaire.

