#### **Applicable visits:**

- 6-months post-transplant visit
- 12-months post-transplant visit
- 13-months post-transplant visit (to be conducted only if, and 1-month after, any original scheduled or rescheduled in-person 12-month post-transplant visit is conducted).

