#### **Procedures:**

- 1. Study staff will identify appropriate participants affected by the cancellation/deferral of regularly scheduled study visits.
- 2. Eligible participants will be contacted by phone and procedures will be explained by the study investigators and staff.
- 3. Participants will be administered the remote consent as per COVID-19 remote consent procedures approved by the CIRB. (see 'Appendix H')
- 4. Staff will interview the participants for review of medical and surgical history, medications, symptom assessment, determination of ECOG performance status, and follow-up questionnaire for the 6-months and 12-months visits.
- 5. Participants will be sent an Evalyn cervical/vaginal specimen collection kit, and a Neoteryx Mitra sampling cartridge. All collection kits will have standardized instructions and study specific information sheets (see 'Finger Stick Participant Information material' and 'Vaginal Self-Collection Instructions'). All devices and return collection kits will have barcoded labels that confidentially link back to the participant record without any identifying information (participant name, other contact details, etc.).
- 6. Participants will self-collect a personal cervical/vaginal specimen and a finger stick blood specimen and will return to the Cedars Sinai biorepository using pre-labeled, pre-paid packages that will be picked up by a courier at the participant's home or pre-arranged location.

- 2. **Expansion of window for 12-months post-transplant visit for specimen collection for primary endpoint:** The visit for specimen collection for the primary endpoint (12-months post-transplantation time point) is regularly scheduled at 12-months +/- 2 weeks after the transplant surgery. The +/- 2 weeks window will now be extended to *up to +/- 6 months* to permit maximum operational flexibility due to the scheduling challenges due to COVID-19, and may be rescheduled to a convenient date and time once it is considered safe to resume study activities.
- 3. **6-months post-transplant study visits:** The rescheduled 12-month post-transplant visit (for the primary endpoint) now includes a very broad/expanded window (+/- 6 months) that may overlap with the original 6-month post-transplant visit timeframe. The 6-month post-transplant visit will therefore be considered an optional one due to the COVID-19-related scheduling challenges.

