- 4. **13-months post-transplant study visits**: This visit will also be considered an optional one and can now be rescheduled to occur one month (+/- 2 weeks) after the rescheduled 12-month post-transplant visit, only for participants who have received the booster injection.
- 5. **Visit procedures:** All procedures in Section 7 "CLINICAL EVALUATIONS AND PROCEDURES" corresponding to the rescheduled visits will be conducted as outlined. In addition, cervical/vaginal, and blood specimens may occur for eligible and consenting participants for the 6-months, 12-months, and 13-months (finger stick only) post-transplant visits.
- 6. **Specimen Management:** The finger-prick collection method will yield dried blood spot collection that will be stored in the biorepository at Cedars Sinai Medical Center for future analysis for the HPV serological analysis for the primary and secondary endpoints. The cervical/vaginal specimens will be used per protocol for analysis of secondary aims.
- 7. **Participant reimbursement**: For participants seen under the COVID-19 Contingency Plan compensation will be per protocol.

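### Does the primary endpoint lack a positivity rule for home dried blood spots, the fallback assay and a ninth HPV type?

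*Combined protocol and SAP*

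**What the plan says.** Section 9.1.1 sets the rule for the primary endpoint. By Merck's cLIA, "a participant will be defined as seroconverted i.e., anti-HPV 6, 11, 16, 18, 31, 33, 45, 52, or 58 positive" is decided type by type, "if the anti-HPV serum level at the 12-months posttransplant visit is" at or above a cut-off in milli Merck units per mL. As read from the PDF, the cut-offs are 30, 16, 20, 24, 10, 8, 8 and 8, matched to the types in order. The section adds that "the seroconversion for each vaccine-serotype will be assessed independently".

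Sections 2.3, 9.1.1 and 10.1.1 allow a nine-valent multiplex assay from the Frederick National Laboratory if the cLIA cannot be used. It is described as validated and as resting on the same principle. Its cut-offs are not printed.

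In Appendix G, item 1 adds a remote option: "we include an at-home finger stick capillary blood collection of a dried blood spot via a novel sample collection device". The 6-, 12- and 13-month post-transplant visits are listed as applicable. Item 2 widens the in-person window for the primary specimen, and item 3 repeats this: "The rescheduled 12-month post-transplant visit (for the primary endpoint) now includes a very broad/expanded window (+/- 6 months"). Item 5 keeps the Section 7 procedures at rescheduled visits and continues: "In addition, cervical/vaginal, and blood specimens may occur for eligible and consenting participants for the 6-months, 12-months, and 13-months (finger stick only"). Item 6 stores the spots for serology for the primary and secondary endpoints.

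Section 10.2.1 has serology run as a batch at the end of the study. Section 13.4 expects 24 to 28 evaluable participants and limits the primary analysis to an estimate with an exact confidence interval, with no benchmark comparison.

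**The concern.** Each type-specific rate rests on its own threshold, and the only printed thresholds are for serum by cLIA. A dried capillary spot is not serum, and Appendix G gives neither a cut-off for it nor a conversion to a serum-equivalent level. If the fallback assay were used, the printed values in Merck units would not obviously carry over, and that would affect every participant.

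The plan also lets one participant have both a spot near month 12 and a serum draw up to six months away, without saying which counts. On top of this, nine types are named against eight values, so on an in-order reading HPV 58 has none.

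Two things would be at stake. Spots read against serum limits could be misclassified. A cut-off chosen after the titres were seen would mean the primary rate was no longer prespecified. With 24 to 28 participants, a few reclassified results would be visible in the estimate.

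**Working it through.** **1. Count of cut-offs (Section 9.1.1).** Types named: 6, 11, 16, 18, 31, 33, 45, 52, 58, which is 9. Values in the text as read: 30, 16, 20, 24, 10, 8, 8, 8, which is 8. Shortfall: 9 − 8 = 1. The values come through as a broken formula string ending in a run of identical terms, where a repeat is easily lost. If the lost value is another 8 in that run, the in-order values for HPV 6 to 52 do not change and HPV 58 takes 8. If it was lost elsewhere, the pairings shift. The text cannot settle this; the source PDF can.

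**2. Search for other rules.** Sections 9.1.1 and 13 and Appendix G contain no threshold or conversion for spots and no threshold for the fallback assay. They also contain no instruction to apply the serum cut-offs to spots.

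**3. How the pieces fit.**
- The printed rule is limited to a serum level at the 12-month visit, so it does not by its own terms reach spots.
- The fallback is worded as a replacement for the whole study, and serology is batched at the end. One assay with one set of validated cut-offs is the natural reading.
- Appendix G opens by saying its adaptations are there so that the trial can meet its primary endpoint. The wider window protects the serum draw; the spot covers participants who cannot attend near month 12.
- The Appendix G condition that "any original scheduled or rescheduled in-person 12-month post-transplant visit is conducted" governs when the 13-month visit may take place. It does not itself show two specimens at month 12. Item 5 is what makes that possible.

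**4. Largest possible effect of the spots.** Let k be the number of participants with only a spot at month 12. The documents do not give k; I assume a range of 0 to 4. The largest shift in one type's rate is k/n, reached only if every spot is misread in the same direction.

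| k | n = 24 | n = 28 |
|---|---|---|
| 0 | 0 | 0 |
| 1 | 1/24 = 4.2 points | 1/28 = 3.6 points |
| 2 | 2/24 = 8.3 points | 2/28 = 7.1 points |
| 4 | 4/24 = 16.7 points | 4/28 = 14.3 points |

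For example, moving from 22/24 to 20/24 changes the estimate from 91.7% (exact 95% CI 73.0 to 99.0) to 83.3% (62.6 to 95.3).

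**5. Price of excluding spot-only participants.** Clopper-Pearson two-sided 95% limits are the 0.025 quantile of Beta(x, n−x+1) and the 0.975 quantile of Beta(x+1, n−x). I assume about 90% positive and that all those excluded are positive.

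| Excluded | From n = 24 | Width | From n = 28 | Width |
|---|---|---|---|---|
| 0 | 22/24: 73.0 to 99.0 | 26.0 | 25/28: 71.8 to 97.7 | 26.0 |
| 2 | 20/22: 70.8 to 98.9 | 28.0 | 23/26: 69.8 to 97.6 | 27.7 |
| 4 | 18/20: 68.3 to 98.8 | 30.5 | 21/24: 67.6 to 97.3 | 29.7 |

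For k of 2 to 4, exclusion costs roughly 2 to 4.5 points of interval width. That is modest, but it comes from a sample already cut from a planned 64.

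**The case for a change.** The strongest case for a change is that Appendix G names the primary endpoint when it stores the spots, so they are not merely kept for later research. Describing the fallback assay as validated and similar in principle says nothing about its units or thresholds, and even with no spots at all that gap could touch every participant. The home option covers only post-transplant visits, so a spot at month 12 may be paired with a serum baseline in the sensitivity analysis restricted to type-specific baseline seronegatives. Section 13.4 offers the results for comparison with other studies, which needs a clear positivity definition. Because serology is batched at the end, the details could be settled cheaply before results are released.

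Most of this stands as description. The spot and fallback thresholds are not printed, and no order of precedence is given. What does not follow is that the plan yields a wrong result. No stated rule misclassifies anyone, and nothing suggests that thresholds would be picked after the titres are seen.

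The firmer remedies carry costs of their own. Always preferring serum would choose a draw up to six months off target over a spot taken nearer month 12. Barring spots without a validated conversion would either remove participants from a set of 24 to 28 or require a bridging study, which works against the reason Appendix G gives for adding them.

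**Conclusion.** No change to the plan is needed. The unprinted thresholds are a gap that competent analysts fill in the ordinary way, by applying the validated cut-offs of the assay actually run. The eight-for-nine count is a matter for the source PDF and, given the broken string, cannot be held against the plan. The choice between an on-time spot and a late or early serum draw is a fair trade-off, and neither order is plainly better.

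The size is bounded but unknown. It is zero if nobody has only a spot. It is at most 8.3 points at 2 of 24 and 16.7 points at 4 of 24, and those bounds need every spot to be wrong in the same direction. The counts of 0 to 4 are assumed, not documented. Because the revised primary analysis describes a rate and its interval without a benchmark, no decision depends on it.

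The conclusion rests on one assay serving the whole study and on spots being read by a method suited to them. Good reporting would name the assay and its cut-offs, say how any 12-month spots were handled, and show the rate without spot-only participants if there are any. Analysts can do this within the plan as it stands.

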# 9.2 Comparable Methods

Proposed methods represent standard technology for HPV detection and genotyping and assessment of HPV antibodies.

#### 10. SPECIMEN MANAGEMENT

#### 10.1 Laboratories

**10.1.1 Blood samples for HPV serology** will be tested at Merck Research Laboratories through support from the Merck Investigator Studies Program (MISP) and an agreement between Merck and NCI DCP or at the National Cancer Institute's Frederick National Laboratory for Cancer Research (FNLCR).

10.1.2 Laboratory for testing the urine, cervical/vaginal, and oral samples for HPV detection and genotyping will be finalized in consultation with the study sponsor, National Cancer Institute-Division of Cancer Prevention.

## 10.2 Collection and Handling Procedures

**10.2.1 Blood samples.** A 28 mL blood specimen will be collected from each participant at the Pre-Transplant Vaccine Visits 1, 2, and 3, at the 6 Month and 12 Month Post-Transplant Visits, and (for participants who do not complete Pre-Transplant Vaccine Visit 2) before/at transplant surgery for measurement of the primary and secondary endpoints for the study. The blood will be collected using four blood collection tubes, including one 10 mL heparin green top tube, two 4 mL EDTA lavender top tubes, and one 10 mL red top tube. A 10 mL blood specimen will be collected at the 13 Month Post-Transplant Visit into one red top tube to measure HPV vaccine-type-specific antibody titers. The blood samples will be processed as specified in the Laboratory Manual and will be separated into plasma, serum, red blood cells, and buffy coat for DNA extraction. These blood components will be transferred to cryovials and will be stored at -80°C. Centrifugation and aliquoting will be done as soon as is feasible (recommended < 2 hours) after the blood draw to allow the samples to be frozen quickly and maintained frozen until thawed and tested. All blood samples will be shipped to CSMC for batch HPV serology at the end of the

study and long-term storage.

- **10.2.2 Cervical/vaginal and oral samples** will be self-collected at the Pre-Transplant Vaccine Visits 1, 2, and 3, and at the 6 Month and 12 Month Post-Transplant Visits for HPV DNA testing. Samples will be collected and processed as specified in the Laboratory Manual. Cervical/vaginal samples will be self-collected using the Evalyn Brush® (Rovers Medical Devices B.V., Oss, Netherlands). Oral samples will be self-collected using a mouthwash gargle. All specimens will be shipped to CSMC as specified in the shipping instructions and will be stored in a -80°C freezer for batch HPV detection and genotyping at the end of the study.
- **10.2.3 Urine samples** will be self-collected at the Pre-Transplant Vaccine Visits 1, 2, and 3, and at the 6 Month and 12 Month Post-Transplant Visits from participants who consent to the collection of optional urine samples. Approximately 20-30 mL of urine (first void catch) will be self-collected at each visit in a sterile urine specimen container. All specimens will be shipped to CSMC as specified in the shipping instructions and will be stored in a -80°C freezer for batch HPV detection and genotyping at the end of the study.
- **10.2.4 Eyebrow hair samples** will be collected at the Pre-Transplant Vaccine Visits 1, 2, and 2, and at the 6 Month and 12 Month Post-Transplant Visits from participants who consent to collection of optional samples for biobanking for future studies. Clinical research staff will collect a total of six eyebrow hairs with the attached follicle from each consenting participant using sterile tweezers and place in a cryovial. Eyebrow hair samples will be shipped to CSMC as specified in the shipping instructions and will be stored in a -80°C freezer for future viral DNA testing.
- **10.2.5 Male genital samples** will be collected at the Pre-Transplant Vaccine Visits 1, 2, and 2, and at the 6 Month and 12 Month Post-Transplant Visits from male participants who consent to collection of these optional samples. Samples will be collected and processed as specified in the Laboratory Manual.

## 10.3 Shipping Instructions

Samples collected from all study sites will be shipped to the CSMC specimen manager. Please see the study's Laboratory Manual for the shipping address.

All processed blood and non-blood samples (cervical/vaginal, oral, urine, and eyebrow) will be shipped overnight in dry ice. All samples will be shipped on Monday or Tuesday in compliance with the International Air Transport Association (IATA) Dangerous Goods Regulations.

## 10.4 Tissue Banking

Biologic specimens collected during the conduct of each clinical trial that are not used during the course of the study will be considered deliverables under the contract and thus the property of the NCI. At study completion, NCI reserves the option to either retain or relinquish ownership of the unused biologic specimens. If NCI retains ownership of specimens, the Contractor shall collect, verify, and transfer the requested biologic specimens from the site to a NCI-specified repository or laboratory at NCI's expense.

# 11. REPORTING ADVERSE EVENTS

DEFINITION: AE means any untoward medical occurrence associated with the use of a drug in humans, whether or not considered drug related. An AE can therefore be any unfavorable and unintended sign, symptom, or disease temporally associated with participation in a study, whether or not related to that participation. This includes all deaths that occur while a participant is on a study.

Please note that all abnormal clinical laboratory values that are determined to be of clinical significance

based on a physician's assessment are to be reported as AEs. Those labs determined to be of no clinical significance or of unknown clinical significance (per the physician's assessment) should not be reported as AEs. Any lab value of unknown clinical significance should continue to be investigated/followed-up further for a final determination, if possible.

A list of AEs that have occurred or might occur can be found in §6.2 Reported Adverse Events and Potential Risks, as well as the Investigator Brochure or package insert.

Each center has the capacity to link to the electronic medical record enabling study personnel to monitor adverse outcomes. Although there is variability in the frequency of post-transplant follow-up and monitoring at the five participating transplant centers, all centers obtain a metabolic panel (BMP) and urinalysis at 6 months, 1 year, and at 2 years post-transplant, as required by the United Network for Organ Sharing (UNOS). Declining renal function is tracked via creatinine levels and allograft rejection is monitored via biopsy when clinically indicated; although one participating center, UCSF, does perform protocol biopsies post-transplant at 6 months and another biopsy at 1 year if the initial biopsy demonstrates inflammation. Data related to post-transplant infectious (bacterial, viral, and fungal) and rejection episodes will be collected as a part of this study.

Postoperative complications, including biopsy-confirmed graft rejection, recurrent kidney disease, and post-transplant infections, will be monitored by the renal transplant teams. Patients receiving additional immunotherapy to treat graft rejection or experiencing post-transplant infectious complications during the study period will be monitored. Standardized definitions will be developed by the investigative team, including nosocomial infections and common opportunistic viral infections [36].

